1. OBJECTIVES

1.1 Primary

The primary objective is to compare carfilzomib, dexamethasone, and daratumumab (KdD) to carfilzomib and dexamethasone (Kd) in terms of progression free survival (PFS) in patients with multiple myeloma who have relapsed after 1 to 3 prior therapies.

1.2 Secondary

[figure not shown]
Key secondary objectives are to compare the following between the 2 arms:

- Overall Response Rate (ORR; defined as the proportion of best overall response of stringent complete response [sCR], complete response [CR], very good partial response [VGPR], and partial response [PR])
- rate of minimal residual disease negative-complete response (MRD[-]CR) in bone marrow aspirates at 12 months (\pm 4 weeks) as determined by Next-Generation sequencing (NGS)
- overall survival (OS)

Additional secondary objectives are to compare the following between the 2 arms:

- safety and tolerability
- duration of response (DOR)
- time to next treatment
- time to progression (TTP)
- time to response
- persistence of MRD[-]CR
- complete response rate (CRR)
- MRD[-] rate
- quality of life

1.3 Exploratory

2. BACKGROUND AND RATIONALE

2.1 Multiple Myeloma

Multiple myeloma, a clonal neoplastic proliferation of plasma cells, is the second most common hematologic malignancy and is responsible for approximately 80000 annual deaths worldwide (1% of cancer deaths). The estimated incidence of multiple myeloma in 2012 worldwide was 114000 persons and this represents 0.8% of all cancers. The 5 year prevalence of multiple myeloma worldwide was estimated at 229000 persons (Ferlay et al, 2015). Multiple myeloma is a disease of older adults, with a median age at diagnosis of 70 years (Howlader et al, 2013).

2.2 Proteasome Background

The proteasome is a multicatalytic proteinase complex that is responsible for degradation of a wide variety of protein substrates within normal and transformed cells. Intracellular proteins targeted for degradation by the proteasome are first ubiquitinated via the ubiquitin conjugation system. Ubiquitinated proteins are cleaved within the proteasome by 1 or more of 3 separate N terminal threonine protease activities: a chymotrypsin like activity, a trypsin like activity, and a caspase like activity.

2.3 Amgen Investigational Product Background

2.3.1 Carfilzomib Background (Nonclinical)

Carfilzomib is a tetrapeptide epoxyketone based inhibitor of the 20S proteasome. Carfilzomib, showed less off target activity when measured against a broad panel of proteases including metallo-, aspartyl-, and serine proteases compared to bortezomib; bortezomib showed off target inhibitory activity in the nanomolar range against several

serine proteases (Arastu-Kapur et al, 2009). This selectivity may be responsible for the reductions in myelosuppression and neuropathy observed in studies comparing carfilzomib with bortezomib.

Incubation of hematologic tumor cell lines with carfilzomib for as little as 1 hour led to rapid inhibition of proteasome activity followed by accumulation of polyubiquitinated proteins and induction of apoptotic cell death (Suzuki et al, 2011; Kuhn et al, 2007).

Carfilzomib has also been administered to rats and monkeys for 6 and 9 months, respectively (twice weekly for 3 weeks on a 28-day cycle). Carfilzomib was well tolerated at doses resulting in more than 80% proteasome inhibition, with no behavioral or histological evidence of peripheral neuropathy (PN) and no neutropenia (Onyx data on file and Carfilzomib Investigator's Brochure [IB]).

2.3.2 Carfilzomib Background (Clinical)

Carfilzomib entered clinical studies in September 2005. On 20 July 2012, Kyprolis® (Carfilzomib for Injection) was approved under the United States Food and Drug Administration's (US FDA) accelerated approval program for the treatment of patients with multiple myeloma who have received at least 2 prior therapies, including bortezomib and an immunomodulatory drug (IMiD), and have demonstrated disease progression on or within 60 days of completion of the last therapy. The initial accelerated approval was based on the results of the phase 2 PX-171-003-A1 study in the United States.

Subsequent full approval in the United States and globally were based on 2 phase 3 trials: PX 171-009 ASPIRE and 2011-003 ENDEAVOR. Following these approvals, Kyprolis in combination with either lenalidomide and dexamethasone or dexamethasone alone is indicated for treatment of relapsed or refractory multiple myeloma (RRMM). The exact indication wording varies by region. Additional data is summarized in the IB.

As of 19 July 2020, an estimated **4361** subjects (**3976.4** subject-years) have been exposed to carfilzomib in company-sponsored clinical trials since the beginning of the development program.

Refer to Section 4 of the Carfilzomib IB for additional information related to the physical, chemical, and pharmaceutical properties and formulation(s).

2.4 Non-Amgen Medicinal Product Background

2.4.1 Daratumumab Background (Non-Amgen Investigational Product)

Daratumumab is a first in class human anti-cluster differentiation antigen 38 (CD38) immunoglobulin (Ig) G1 (kappa) monoclonal antibody. CD38 is differentially expressed

during B-cell development with greatest expression on terminally differentiated B-cells. CD38 is an enzyme that catalyzes the metabolism of cyclic adenosine diphosphate ribose and nicotinic acid to adenosine diphosphate which functions in regulation of intracellular calcium stores. Various preclinical experiments with multiple myeloma cell lines, purified multiple myeloma cells, and mononuclear cell suspensions have demonstrated that daratumumab triggers lysis of multiple myeloma cells by a variety of mechanisms. The binding of the antibody to CD38 positions of the Fc receptor (FcR) in a way that optimizes interaction with complement resulting in strong complement dependent lysis (de Weers et al, 2011).

Antibody dependent lysis with daratumumab has been demonstrated in complement free cell suspensions of multiple myeloma cells and cell lines with peripheral blood mononuclear cells (PBMCs) enriched for natural killer (NK) cells using both normal and patient PBMCs. Other mechanisms of action (MoA) including antibody-dependent cellular phagocytosis (ADCP) and apoptosis triggered by FcR-crosslinking have been demonstrated with daratumumab (van der Veer et al, 2011b). Analysis from clinical trials of daratumumab revealed an immunomodulatory role of daratumumab that leads to the induction of clonal T cell expansion and reduction of immune suppressive cell populations CD38⁺ myeloid-derived suppressor cells (MDSC), CD38⁺ TReg, and CD38⁺ BReg cells (Krejci et al, 2016).

Clinical activity of daratumumab was first studied in phase 1/2 Gen 501 and phase 2 SIRIUS trials. A recent summary of the pooled results of these trials was reported (Usmani et al, 2016). The patient population was RRMM with 2 or more prior lines of therapy, 76% of patients received more than 3 lines of therapy (median 5, range 2 to 14 lines). A total of 148 patients were treated at the 16 mg/kg dose, 86.5% of patients were double refractory to both IMiD and proteasome inhibitors. The ORR was 31% and DOR 7.6 months with a median PFS of 4 months. Only 4% of patients discontinued therapy due to adverse events. Most adverse events were due to infusion reactions with approximately 50% with reactions to first infusion dropping to approximately 10% with second infusion and rare with subsequent infusions. Of interest, patients achieving only stable disease/minimal response (SD/MR) also appeared to benefit with a median OS of 18 months compared to 20 months for responders and 3 months for those with not evaluable/progressive disease (NE/PD). The highly significant activity of daratumumab in RRMM, novel non-overlapping mechanism or

toxicity with regard to bortezomib and lenalidomide predict high tolerability and efficacy of KdD combination therapy in treatment of relapsed multiple myeloma.

[figure not shown]
2.4.2 Daratumumab Mechanism of Action

Daratumumab is a targeted immunotherapy that binds to CD38, a transmembrane glycoprotein that is overexpressed in multiple myeloma plasma cells. Multiple MoA have been observed for daratumumab, including complement dependent cytotoxicity (CDC), antibody-dependent cellular cytotoxicity (ADCC), induction of apoptosis by Fc gamma receptor mediated crosslinking of tumor bound monoclonal antibodies, and ADCP.

Translational biomarker studies of samples from patients treated in daratumumab phase 1 and phase 2 studies (Studies GEN501 and MMY2002, respectively) have revealed previously unknown immunomodulatory effects of daratumumab (Krejci et al, 2016). Detailed analysis by flow cytometry (FC) of changes in circulating immune cells demonstrated that daratumumab was able to induce large increases in CD8⁺ T numbers. Next generation T-cell receptor (TCR) sequencing was utilized to evaluate changes in T cell clonality. Interestingly, in patients who responded to daratumumab, both the maximal individual increase in a T cell clone, as well as the sum of expanded T cell clones, were significantly increased suggesting that T cell expansion may have a role in eliminating the myeloma cells. In order to assess the potential mechanism by which daratumumab could lead to these increases in T cell clones, additional analysis revealed that there was a rapid and sustained elimination of highly immunosuppressive subsets of CD38⁺ Tregs, CD38⁺ MDSCs, and CD38⁺ Bregs in patients treated with daratumumab. The CD38⁺ Tregs identified is a novel population of Tregs that are more immunosuppressive than CD38⁻ Tregs. In addition, it has also been shown that daratumumab can modulate the enzymatic activity of CD38 and potentially lead to a reduction in immunosuppressive adenosine levels in the tumor microenvironment (Horenstein et al, 2013).

Some of daratumumab's most differentiating attributes are the depth of response achieved in responders and the drug's multifaceted MoA. Based upon these new findings, it is hypothesized that daratumumab's deep and durable responses in patients with multiple myeloma are induced, in part, by the immunomodulatory activity that removes immune suppressive functions of CD38⁺ MDSC, CD38⁺ TReg, and CD38⁺ BReg cells and increases T cell clonality. A figure summarizing daratumumab's novel, converging MoA is presented in [Figure 1](#).

Figure 1. Daratumumab Mechanisms of Action

ADCC = antibody dependent cellular cytotoxicity; ADPC = antibody dependent cellular phagocytosis; ADPR = adenosine diphosphate ribose; AMP = adenosine monophosphate; Ca^{2+} = calcium ion; cADPR = cyclic adenosine diphosphoribose; CD38 = cluster differentiation antigen 38; $CD8^{+}$ = cluster of differentiation 8; CDC = complement-dependent cytotoxicity; DARA = daratumumab; MM = multiple myeloma; MDSC = myeloid-derived suppressor cell; NAADP = nicotinic acid adenine dinucleotide phosphate; NAD = nicotinamide adenine dinucleotide; NK = natural killer.

Previously reported to kill tumor cells by immune-mediated mechanisms, such as ADCC, ADPC, and CDC, as well as by programmed cell death via cross linking of the antibody on the cell surface, it is now known that daratumumab also induces immunomodulatory effects via several different pathways that contribute to killing of $CD38^{+}$ immune cells that modulate T cell activity, namely MDSC, TReg, and BReg. This is a novel mechanism previously unreported that is hypothesized to drive development of multiple opportunities for daratumumab beyond $CD38^{+}$ myeloma and other heme malignancies.

2.4.3 Dexamethasone (Non-Amgen Non-investigational Product)

Dexamethasone is commercially available. Details regarding the description, supply, and storage instructions for dexamethasone are found in the prescribing information. Sites are advised to refer to the prescribing information for information that is specific to the brand or formulation of the drug product in use.

2.5 Rationale

2.5.1 Study Rationale

Relapsed or refractory multiple myeloma treatment has evolved rapidly in recent years. ASPIRE was the first phase 3 randomized study demonstrating that a triplet using non-conventional chemotherapy agents had significant improvement in outcomes when compared with a duplet. In this study, KRd reduced the risk of progression by 31% when compared to lenalidomide and dexamethasone (hazard ratio [HR] = 0.69, $P < 0.0001$; Stewart et al, 2015) which translated in a median PFS of 26.3 months in the KRd arm with consistent benefit in subgroup analyses. These positive results were despite limiting carfilzomib treatment to the first 18 cycles of therapy. Soon after, the concept of superior outcomes with novel agent-based triplets as treatment of early relapsed multiple myeloma (1 to 3 prior lines) was confirmed with other combinations (Table 1). More recently, interim data from 2 phase 3 trials with daratumumab has shown improvement of outcomes when added to either bortezomib and dexamethasone or lenalidomide and dexamethasone backbones. Compared to lenalidomide and dexamethasone for patients with RRMM with a median of 1 prior line of therapy, the addition of daratumumab reduced the risk of progression by 63% (HR = 0.37, $P < 0.0001$; Dimopoulos et al, 2016). Compared to bortezomib and dexamethasone, the addition of daratumumab reduced the risk of progression by 61% in patients with RRMM with a median of 2 prior lines of therapy (HR = 0.39, $P < 0.0001$; Palumbo et al, 2016).

Among the phase 3 studies in relapsed multiple myeloma, the results achieved with carfilzomib and daratumumab based combinations suggest that these 2 agents are likely the most potent in their respective classes. They both have demonstrated high rates of overall responses and significant increment of CRRs (Table 1). Moreover, pre-clinical and clinical studies combining daratumumab to proteasome inhibitors have demonstrated synergy (Palumbo et al, 2016; van der Veer et al, 2011a). Therefore, it is expected that the combination of both agents, carfilzomib and daratumumab, would provide a highly efficacious treatment option for patients with relapsed disease.

A number of ongoing phase 3 studies in newly diagnosed transplant ineligible patients are evaluating lenalidomide-based triplets with planned treatment to continue until progression (NCT01335399, NCT01850524, NCT02252172, and NCT02579863). Moreover, a recent meta-analysis has demonstrated OS advantage on the use of lenalidomide maintenance after autologous stem cell transplant (McCarthy et al, 2016). This information points to an increase in the number of subjects that have been exposed

to lenalidomide in first line. Developing lenalidomide-sparing options is expected to address a significant unmet need in the near future for the treatment of relapsed myeloma.

Table 1. Response Rates and Progression Free Survival in Recent Relapsed Multiple Myeloma Phase 3 Clinical Trials

Trial	Arm	ORR (%)	CR (%)	PFS (mo)
ENDEAVOR	Kd	77%	13%	18.7
	Vd	63%	6%	9.4
ASPIRE	KRd	87%	31.8%	26.3
	Rd	67%	9%	17.6
CASTOR	DVd	83%	19%	NR
	Vd	63%	9%	7.3
POLLUX	DRd	93%	43%	NR
	Rd	76%	19%	18.4
ELOQUENT-II	Elotuzumab Rd	79%	4%	19.4
	Rd	66%	7%	14.9
TOURMALINE-II	Ixazomib Rd	78%	11.7%	20.6
	Rd	71.5%	6.6%	14.7

CR = complete response; d = dexamethasone; D = daratumumab; K = carfilzomib; mo = month; NR = not reached; ORR = overall response rate; PFS = median progression-free survival; R = lenalidomide; V = bortezomib.

2.5.2 Rationale for Daratumumab Dose

Dosing of daratumumab in subjects with multiple myeloma is recommended at 16 mg/kg (weekly for 8 weeks, then every 2 weeks for 16 weeks, then every 4 weeks thereafter) administered via intravenous (IV) until disease progression or unacceptable toxicity. The dose selection was based on an acceptable safety profile, maximal clinical activity, and PKs consistent with saturation of the target. The data supporting the selection of a 16 mg/kg dose for the treatment of multiple myeloma are as follows:

- Safety: Clinical safety data demonstrated that daratumumab is well-tolerated, with clinically manageable side effects, highlighted by the fact that no subject treated with 16 mg/kg daratumumab monotherapy discontinued treatment as a result of a daratumumab related adverse event.
 - For doses above 4 mg/kg, there was no dose dependent toxicity pattern observed.

- Clinical efficacy: Clinical response data derived from Study GEN501 and Study MMY2002 show robust activity among subjects treated at 16 mg/kg with ORRs of 36% and 29%, respectively.
 - The response rates were consistently and significantly higher and deeper at the 16 mg/kg dose level as compared to various schedules at the 8 mg/kg dose level.
- Pharmacokinetics: Daratumumab exhibits target-mediated drug disposition. Daratumumab binds to CD38 receptors in the body and the complex with daratumumab is rapidly cleared. As the dose is increased or after repeated administration, CD38 becomes saturated, and the impact of target binding clearance is minimized and PK data can indicate target saturation.
 - Population PK and exposure-response analyses suggested that 16 mg/kg is the lowest tested dose at which the majority (approximately 80%) of subjects achieved serum concentrations above the model-predicted 99% target saturation threshold and 90% of the maximum effect on ORR threshold.
 - Lowering the dose would likely result in reduced efficacy, whereas increasing the dose may not provide further improvement of the benefit-risk profile.
 - The initial weekly dosing schedule rapidly established efficacious concentrations. The every 2 week and every 4 week dosing frequencies were sufficient to produce serum concentration levels that maintained target saturation; thus reducing the risk of disease progression.

2.5.3 Rationale for the Combination

The rationale for combining daratumumab with a proteasome inhibitor is supported by the results obtained in the CASTOR study as described above. This study was conducted with bortezomib, a reversible inhibitor of the proteasome which was also evaluated head-to-head against carfilzomib and dexamethasone in the ENDEAVOR study with a similar patient population. The results of this comparison suggest superior outcomes with carfilzomib with a 47% reduction in the risk of progression or death (HR = 0.53, $P < 0.0001$; Dimopoulos et al, 2016) and are the basis for the labeled dose in RRMM. Given the orthogonal MoA of daratumumab, the addition to the carfilzomib and dexamethasone regimen is hypothesized to be highly efficacious and possibly result in a longer duration of PFS compared to the experimental arm in the CASTOR study. An ongoing phase 1b study is evaluating the safety of the addition of daratumumab to carfilzomib and dexamethasone (NCT01998971). As of 30 June 2016, 20 subjects have been treated with KdD in the ongoing Study MMY1001. The most frequently reported grade 3 or 4 adverse events were laboratory-related and included thrombocytopenia (35%), neutropenia (25%), and anemia (15%). Cardiac disorders were reported in 4 subjects and were grade 1 and 2 tachycardia (2 subjects), atrial fibrillation (1 subject), and cardiac failure (1 subject). No grade ≥ 3 cardiac disorder adverse events were

reported. The subject with grade 2 cardiac failure recovered from the event and continued on investigational product, receiving a reduced dose of carfilzomib. Based on these preliminary data, the combination of KdD is well tolerated with a safety profile that is consistent with the known safety profile of daratumumab or Kd.

For the combination of these 2 agents, the initial daratumumab infusion and any subsequent infusions that would otherwise require a large volume (eg, 1 liter); will be divided in 2 days to minimize the risk of volume overload given that new or worsening cardiac failure has occurred following the administration of carfilzomib.

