6.2.2 Non-Amgen Investigational Product: Daratumumab

6.2.2.1 Daratumumab: Dosage, Administration, and Schedule

Daratumumab will be administered as an IV infusion. On days when more than 1 investigational products are administered, the required administration is as follows: dexamethasone, other pre-infusion medications for daratumumab, carfilzomib, daratumumab, and post-infusion medications for daratumumab.

- On days 1 and 2 of cycle 1, daratumumab will be administered at 8 mg/kg in 500 mL normal saline each day.
 - If the subject's first 2 infusions of 8 mg/kg daratumumab are well-tolerated (defined as an absence of infusion-related reaction [IRR] > grade 1), the first infusion of 16 mg/kg in 500 mL normal saline will be given once weekly as a

single infusion for the remaining doses of the first 2 cycles, ie, days 8, 15, and 22 of cycle 1; and days 1, 8, 15, and 22 of cycle 2, then every 2 weeks for 4 cycles (cycles 3 to 6), and then every 4 weeks for the remaining cycles or until disease progression.

- If the 8 mg/kg infusions are not well-tolerated (defined as IRR > grade 1), the dilution will be in 1000 mL of normal saline until the subject completes an infusion without > grade 1 IRR. For any infusions that would require a large volume (eg, 1000 mL); the daratumumab dose may be divided in 2 days.

The administration may be within \pm 2 days for each scheduled dose. See [Table 13](#) to review the arm 1 dosing schedule.

Each subject's dose will be calculated based on the subject's weight rounded to the nearest kilogram. Dosing calculations do not need to be changed for weight changes that are < 10% from baseline. The pharmacist will calculate the required volume and number of vials needed. The daratumumab infusion rates are provided in [Table 5](#) and [Table 6](#).

The planned dose (mg/kg), dose (mg), start date/time, stop date/time, reason for change in planned dose, reason for dose change/withheld, reason for dose delay, reason for dose interruption and package lot number of daratumumab is to be recorded on each subject's eCRF.

Table 5. Daratumumab Infusion Rate

C1D1 and C1D2 (8 mg/kg)		C1D8 (16 mg/kg)		Subsequent Infusions	
Time (minutes)	mL/hr	Time (minutes)	mL/hr	Time (minutes)	mL/hr
0 – 60	50	0 – 60	50 ^a	0 - 60	100 ^b
61 – 120	100	61 – 120	100	61 - 120	150
121 – 180	150	121 - 180	150	121 - 180	200
181 – 240	200	181 - 240	200	181-	200
500 mL		500 mL ^a		500 mL	

CxDx = cycle X day X; IRR = infusion-related reaction.

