^a If the subject's first 2 infusions of 8 mg/kg daratumumab are well-tolerated (defined as an absence of IRR > grade 1), the first infusion of 16 mg/kg daratumumab will be administered at an initial rate of 50 mL/hour and increased by 50-mL/hour increments at 60-minute intervals, as tolerated, to a maximum rate of 200 mL/hour. If the 8 mg/kg infusions are not well-tolerated (defined as IRR > grade 1), the dose may be split in 2 days (on 500 mL each day).

^b Modified rates should only be used if at least 1 16 mg/kg infusions of daratumumab was well-tolerated as defined by an absence of >grade 1 infusion-related reactions during a final infusion rate of \geq 100 mL/hr.

The duration of infusion may be shortened starting in cycle 2 onwards to a 90-minute infusion for subjects without a history of an infusion related reaction after the third dose of daratumumab.

The 90-minute daratumumab accelerated infusions (Barr et al, 2017) can be administered at an initial rate of 20% of the total dose over 30 minutes, followed by the remaining 80% of the total dose over 60 minutes (90-minute total infusion time).

- Rapid infusion will be given in a total volume of 500 mL
- This allows for a rate of 200 mL/hour for the first 30 minutes and a rate of 400 mL/hour for the final 60 minutes.
- If a subject experiences any grade infusion related reaction, the subject will not be eligible to receive additional rapid infusions until he/she has received standard infusion daratumumab without any grade hypersensitivity reaction.

Table 6. Accelerated/Shortened Infusion Rate

Accelerated/Shortened Infusion	Dilution Volume	Initial Infusion Rate (first 30 minutes)	Subsequent Infusion Rate (last 60 minutes)	Maximum Infusion Rate
	500 mL	200 mL/hour	400 mL/hour	400 mL/hour

Rapid infusion will be given in a total volume of 500 mL. This allows for a rate of 200 mL/hour or the first 30 minutes and a rate of 400 mL/hour for the final 60 minutes. If a subject experiences any grade infusion related reaction, he/she is not eligible to receive additional rapid infusions until they have received standard infusion daratumumab without any grade hypersensitivity reaction.

Source: Barr et al, 2017.

See Section 7.3.10 for details on vital sign monitoring during daratumumab and other infusions.

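### For daratumumab infusions after the initial dose that need about 1 liter, Protocol Section 2.5.3 says the dose will be divided over 2 days, while Section 6.2.2.1 and Table 5 footnote a say only that it may be

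*Protocol*

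**What the plan says.** Protocol Section 2.5.3 ends with a precaution specific to this combination: certain daratumumab infusions "will be divided in 2 days to minimize the risk of volume overload". One sentence covers two cases: "the initial daratumumab infusion and any subsequent infusions that would otherwise require a large volume (eg, 1 liter); will be divided in 2 days". The reason given is "to minimize the risk of volume overload given that new or worsening cardiac failure has occurred following the administration of carfilzomib".

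Section 6.2.2.1 gives the operating rules. For the initial dose: "On days 1 and 2 of cycle 1, daratumumab will be administered at 8 mg/kg in 500 mL normal saline each day". If those infusions bring an IRR above grade 1, a larger volume is directed: "the dilution will be in 1000 mL of normal saline until the subject completes an infusion without > grade 1 IRR". The sentence after that reads: "For any infusions that would require a large volume (eg, 1000 mL); the daratumumab dose may be divided in 2 days".

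Table 5 footnote a, attached to the first 16 mg/kg infusion on cycle 1 day 8, covers the same subjects: "the dose may be split in 2 days (on 500 mL each day".

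The Table 13 note says that after cycle 1 days 1 and 2 each 16 mg/kg dose is diluted in 500 mL. It makes no exception for a larger volume.

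**The concern.** Sections 2.5.3 and 6.2.2.1 describe the same trigger, a later infusion needing about a liter, in nearly the same terms. The verb changes from an obligation to a permission. In Section 6.2.2.1 the larger volume is directed while the measure that limits its daily load is left open.

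Two things are at stake. A site that gives 1000 mL in one day complies with Section 6.2.2.1 but departs from the safety measure in Section 2.5.3. And a reader who relies on Section 2.5.3 when interpreting cardiac findings in the KdD arm would take the 2-day division of large volumes to be uniform, although the dosing section leaves it open. Treatment-emergent adverse events and LVEF are secondary endpoints (Section 10.1.1.2), and Section 7.3.4 calls for additional information on cardiac failure and dyspnea events.

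**Working it through.** The plan states no figure on this point, so there is none to reproduce. The check is a comparison of text plus one line of volume arithmetic.

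| Place in the protocol | Initial dose (cycle 1 days 1 and 2) | Later infusion needing about 1000 mL |
|---|---|---|
| Section 2.5.3 | Divided over 2 days | Division stated as a fixed measure |
| Section 6.2.2.1 | 8 mg/kg in 500 mL on each day | 1000 mL directed; division optional |
| Table 5 and footnote a | 500 mL each day | Division optional, 500 mL on each day |
| Table 13 note | 8 mg/kg in 500 mL on each day | Not covered; 500 mL per 16 mg/kg dose |

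1. **Initial dose.** All four places agree. There is no conflict here.

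2. **Later large-volume infusions.** Section 2.5.3 disagrees with Section 6.2.2.1 and Table 5 footnote a on whether division is required.

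3. **Daily volume.** If divided: 1000 mL / 2 = 500 mL per day. If undivided: 1000 mL in one day. The ratio is 1000 / 500 = 2, so the optional wording allows twice the daily volume implied by Section 2.5.3. The total volume is the same.

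4. **Do the tables settle it?** No. Table 5's rates for cycle 1 days 1, 2 and 8 add up to 50 + 100 + 150 + 200 = 500 mL over four hours, and the table has no column for an undivided 1000 mL infusion. The Table 13 note puts a full 16 mg/kg dose into 500 mL. That describes neither 1000 mL in one day nor 500 mL on each of two.

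5. **Who is affected, and for how long.** Only arm 1 subjects with an IRR above grade 1 on the 8 mg/kg infusions. Section 6.2.2.1 ends the 1000 mL dilution once a subject gets through an infusion without such a reaction.

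6. **Overlap with carfilzomib.** In Table 13, daratumumab and carfilzomib fall on the same day on cycle 1 days 8 and 15. On day 22 no carfilzomib is scheduled. An undivided large-volume infusion would therefore coincide with carfilzomib on some of these days but not all.

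**The case against.** The strongest reply is that Section 2.5.3 is background. Sites dose from Section 6 and its tables, and there Section 6.2.2.1 and Table 5 footnote a agree that division is optional. On that view the mismatch lies between a rationale and an instruction, not between two dosing instructions.

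The protocol also has other protections. Arm 1 needs no carfilzomib prehydration on daratumumab days (Section 6.2.1.1.1). Exclusions 218 and 219 remove subjects who cannot tolerate hydration because of pulmonary or cardiac impairment and those with NYHA Class III to IV heart failure. Inclusion 109 requires LVEF of at least 40%. Table 4 holds carfilzomib for any congestive heart failure. The data monitoring committee's initial assessment comes after 30 subjects have finished cycle 1. Finally, this is Amendment 6, dated 17 March 2021 and written after the primary endpoint was met, so new wording can change little in practice.

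Most of this stands, and it limits the point. It does not remove it. Section 2.5.3 is current text of the same protocol, states the division as something that will happen, and ties it to a named cardiac risk. None of the other protections says whether a 1000 mL infusion must be divided.

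A reader might infer three stronger things that the documents do not support:

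- **That the safeguard justifying the combination was dropped.** The half of the sentence that applies to every KdD subject, the split of the initial dose, is carried through everywhere. Section 2.5.3 rests the combination on two phase 3 trials and a phase 1b study; the split is a precaution added at the end.
- **That a particular number of the 300 arm 1 subjects is affected.** The nearest figure is in Section 2.4.1: about 50% with a reaction at the first infusion, falling to about 10% at the second. It comes from pooled monotherapy studies and gives no grade. The trigger here is a reaction above grade 1 to split, premedicated 8 mg/kg doses given with carfilzomib. No count follows.
- **That KdD cardiac results depend on site practice.** The documents contain nothing that measures such an effect.

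**Conclusion.** The inconsistency is real and minor. For daratumumab infusions after the initial dose that need about 1000 mL, Section 2.5.3 makes division over 2 days a fixed measure. Section 6.2.2.1 and Table 5 footnote a make it optional, and the Table 13 note does not cover the case. The difference is 1000 mL against 500 mL on the first day of an affected infusion.

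The conclusion rests on reading Section 2.5.3 as a statement of what the protocol does, which is how it is worded. The number of subjects affected is not given and cannot be derived. Sample size, power, alpha and the PFS analysis are unaffected. At this stage of the trial, the main benefit of correction is an accurate record of the precaution for anyone interpreting KdD cardiac safety. This review takes no position on which rule is right.

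**What to change.** Reconcile Section 2.5.3, Section 6.2.2.1, Table 5 footnote a and the Table 13 note so that all four state the same rule: whether division of a large-volume infusion is required or optional, and under what condition. The Table 13 note should also acknowledge the large-volume case that Section 6.2.2.1 creates. The clinical team must decide the content of the rule. The text on the initial dose needs no change.

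The cost is protocol wording only, with no change to the SAP.
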